## **11 SOURCE DOCUMENTS AND ACCESS TO SOURCE DATA/DOCUMENTS**

Each participating site will maintain appropriate medical and research records for this trial, in compliance with ICH E6 and regulatory and institutional requirements for the protection of confidentiality of participants.

The clinical site participating in this study are required to submit clinical data for each enrolled subject via an EDC system, using an eCRF. Site personnel will be trained on the EDC system before receiving access to the system. The Sponsor or designee is responsible for maintaining a record of all system users. The participants of the study will not be identified by name on any study documents to be collected by the Sponsor (see [Section 13.4](#)).

All clinical information requested in this protocol will be recorded on the eCRF provided by the CRO (or via other data collection methods, e.g. electronic laboratory data transfer). The principal Investigator is responsible for reviewing all eCRFs, verifying them for accuracy, and approving them via an electronic signature. Copies of the completed eCRFs, saved to disk in .pdf format, will be sent to the Investigator's site at the completion of the study.

Additional source data may include, but are not limited to, hospital records, clinical and office charts, laboratory notes, memoranda, participant's memory aids or evaluation checklists, pharmacy dispensing records, recorded audio tapes of counseling sessions, recorded data from automated instruments, copies or transcriptions certified after verification as being accurate and complete, photographic negatives, and participant files and records kept at the pharmacy, at the laboratories, and medico-technical departments involved in the clinical trial.

## **12 QUALITY ASSURANCE AND QUALITY CONTROL**

See [Section 9](#).

## **13 ETHICS/PROTECTION OF HUMAN SUBJECTS**

### **13.1 Ethical Standard**

The Investigator will ensure that this study is conducted in full conformity with Regulations for the Protection of Human Subjects of Research codified in 45 Code of Federal Regulations (CFR) Part 46, 21 CFR Part 50, 21 CFR Part 56, and/or the ICH E6.

### **13.2 Institutional Review Board**

The protocol, informed consent form(s), recruitment materials, and all participant materials will be submitted to the IRB for review and approval. Written approval of both the protocol and the consent form must be obtained before any participant is enrolled. Any amendment to the protocol will require review and approval by the IRB before the changes are implemented to the study. All changes to the consent form will be IRB approved; a determination will be made regarding whether previously consented participants need to be re-consented.

### **13.3 Informed Consent Process**

The Sponsor must review the draft ICF prepared by the Investigator prior to submission to the IRB for approval. An IRB-approved copy of the ICF will be forwarded to the Sponsor.

The ICF documents the study-specific information the Investigator provides to the subject and the subject's agreement to participate. Among other things, the Investigator will fully explain in layman's terms the nature of the study, along with the aims, methods, potential risks, and any discomfort participation may entail. The subject must sign and date the ICF before any study-related procedures are performed. The original and any amended signed and dated ICF(s) must be retained in the subject's file at the study site and a copy must be given to the subject.

### **13.4 Participant and Data Confidentiality**

The Investigator must ensure that each subject's anonymity is maintained as described below. On the eCRFs or other documents submitted to the Sponsor, subjects must be identified by no more than their initials, date of birth, and a Subject Identification Number. Documents that are not for submission to the Sponsor (e.g., signed ICFs) should be kept in strict confidence by the Investigator in compliance with applicable regulations and ICH GCP E6 Guidelines ([FDA 2015](#)). Participant confidentiality is strictly held in trust by the participating Investigators, their staff, and the Sponsor(s) and their agents. This confidentiality is extended to cover testing of biological samples and genetic tests in addition to the clinical information relating to participants. Therefore, the study protocol, documentation, data, and all other information generated will be held in strict confidence. No information concerning the study or the data will be released to any unauthorized third party without prior written approval of the Sponsor.

The Investigator and institution must permit authorized representatives of the Sponsor, of regulatory agencies, and the IRB direct access to review the subject's original medical records for verification of study-related procedures and data. Direct access includes examining, analyzing, verifying, and reproducing any records and reports that are needed for the evaluation of the study. The Investigator is obligated to inform the subject in the ICF that the above named representatives may review study-related records from subjects.

#### **13.4.1 Research Use of Stored Human Samples or Data**

Samples and data collected under this protocol may be used to study the safety and efficacy of EB-001. All data and materials created from the samples will be the property of the Sponsor. Samples collected will be stored in either the laboratory of the Sponsor or the laboratory of a company contracted to work with the Sponsor with a proper tracking system. Access to study samples will be limited to laboratory personnel working for the Sponsor or contracted to the Sponsor, who are authorized to perform analyses.

Samples collected may be stored for up to 10 years after the end of the study (the end of the study occurs when a final study report is written).

### **13.5 Future Use of Stored Specimens**

Additional tests may be conducted on subject blood samples to better understand or develop treatments for pectoral muscle pain, and/or for safety issues that may arise in the future.

During the conduct of the study, an individual participant can choose to withdraw consent to have biological specimens stored for future research. However, withdrawal of consent with regard to biosample storage will not be possible after the study is completed.

### **13.6 Protocol Amendments and Study Termination**

Protocol amendments must be made only with the prior approval of the Sponsor. Agreement from the Investigator must be obtained for all protocol amendments and amendments to the ICF. The IRB must be informed of all amendments and give approval for any amendments before the changes are implemented to the study. The Investigator must send a copy of the approval letter from the IRB to the Sponsor.

Both the Sponsor and the Investigator reserve the right to terminate the study, according to the study contract. The Investigator should notify the IRB in writing of the trial's completion or early termination and send a copy of the notification to the Sponsor.

## **14 DATA HANDLING AND RECORD KEEPING**

### **14.1 Data Collection and Management Responsibilities**

Data collection is the responsibility of the clinical trial staff at the site under the supervision of the site Investigator. The Investigator is responsible for ensuring the accuracy, completeness, legibility, and timeliness of the data reported.

All source documents should be completed in a neat, legible manner to ensure accurate interpretation of data. Black or blue ink is required to ensure clarity of reproduced copies. When making changes or corrections, cross out the original entry with a single line, and initial and date the change. DO NOT ERASE, OVERWRITE, OR USE CORRECTION FLUID OR TAPE ON THE ORIGINAL.

Data reported in the eCRF derived from source documents should be consistent with the source documents or the discrepancies should be explained and maintained in the participant's official study record.

Clinical data (including AEs, concomitant medications, and expected adverse reactions data) and clinical laboratory data will be entered into Axiom Fusion, a 21 CFR Part 11-compliant data capture system provided by the Axiom Real-time Metrics. The data system includes

password protection and internal quality checks, such as automatic range checks, to identify data that appear inconsistent, incomplete, or inaccurate. Clinical data will be entered directly from the source documents.

## **14.2 Study Records Retention and Availability**

The Investigator must make study data accessible to the study monitor, other authorized representatives of the Sponsor, and Regulatory Agency inspectors upon request. A file for each subject must be maintained that includes the signed ICF and the Investigator's copies of all source documentation related to that subject. The Investigator must ensure the reliability and availability of source documents from which the information on the eCRF was derived.

Investigators are required to maintain all study documentation, including copies of eCRFs, ICFs, and adequate records for the receipt and disposition of all study medications, for a period of 2 years following the FDA or other regulatory approval date of the drug, or until 2 years after the drug investigational program is discontinued, unless a longer period is required by applicable law or regulation. The Investigator must not discard any records unless given authorization by the Sponsor.

Subject identity information will be maintained for 15 years unless applicable law or regulation requires a longer period.

## **14.3 Protocol Deviations**

A protocol deviation is any noncompliance with the clinical trial protocol or GCP requirements. The non-compliance may be either on the part of the participant, the Investigator, or the study site staff. As a result of deviations, corrective actions may be developed by the site and implemented promptly.

These practices are consistent with ICH E6:

- 4.5 Compliance with Protocol, sections 4.5.1, 4.5.2, and 4.5.3
- 5.1 Quality Assurance and Quality Control, section 5.1.1
- 5.20 Noncompliance, sections 5.20.1, and 5.20.2.

All deviations must be addressed in study source documents and transcribed into the eCRF (as applicable). Protocol deviations must be sent to the local IRB per their guidelines. The site Investigator and study staff are responsible for knowing and adhering to their IRB requirements.

## **14.4 Publication and Data Sharing Policy**

All publication and authorship rights are delineated in the Clinical Study Agreement.

Effective Date: 07NOV2018

7.2.1	Primary Efficacy Endpoint	16
7.2.2	Secondary Efficacy Endpoints	16
7.3	Analysis Methods	16
7.3.1	AUC Outcomes	16
7.3.2	NPRS and NPRS-A Outcomes	17
7.3.3	Patient Global Assessment (PGA) of Pain Control	17
7.3.4	Rescue Medication	17

A horizontal bar chart with 12 bars. The bars are black and of varying lengths, decreasing from left to right. The first bar is the longest, followed by a short bar, then a long bar, then a short bar, then a long bar, and finally a very long bar on the far right.

11. INTERIM ANALYSES AND DATA MONITORING	24
12. CHANGES TO THE ANALYSES PLANNED IN THE PROTOCOL	24

Sponsor: Bonti, Inc.
Protocol Number: EB001-ABD201

Statistical Analysis Plan Version 1.0
Effective Date: 07NOV2018

LIST OF IN-TEXT TABLES AND FIGURES

Table 7-1 Table of Morphine Milligram Equivalents 18

[REDACTED]

[REDACTED]

LIST OF ABBREVIATIONS (COMMONLY USED)

ADaM	Analysis Data Model
ADL	Activities of Daily Living
AE	Adverse Event
ANOVA	Analysis of variance
ATC	Anatomical Therapeutic Chemical
AUC	Area Under the Curve
BMI	Body Mass Index
BP	Blood Pressure
CRF	Case Report Form
CSR	Clinical Study Report
CSU	Clinical Study Unit
EB-001	Botulinum Neurotoxin Serotype E Drug Product
ECG	Electrocardiogram
EOS	End of Study
ET	Early Termination
FEV1	Forced Expiry Volume 1
FVC	Forced Vital Capacity
GCP	Good Clinical Practice
HIV	Human Immunodeficiency Virus
HR	Heart Rate
HSA	Human Serum Albumin
ICF	Informed Consent Form
ICH	International Conference on Harmonization
IM	Intramuscular
MedDRA	Medical Dictionary for Regulatory Activities
mitT	Modified Intent to Treat
NPRS	Numerical Pain Rating Scale
NPRS-A	Numerical Pain Rating Scale Administered After an Activity
MEQ	morphine milligram equivalents

PACU	Post-Anesthesia Care Unit
PFT	Pulmonary Function Test
PGA	Patient Global Assessment
PP	Per Protocol
PR Interval	Time between the onset of atrial depolarization and the onset of ventricular depolarization
PT	Preferred Term
QRS duration	The interval from the beginning of the Q wave to the termination of the S wave, representing the time for ventricular depolarization
QT Interval	Interval representing the time for both ventricular depolarization and repolarization to occur
QTcB Interval	QTc interval using Bazett's correction (msec) = $QT/(RR)^{1/2}$, where the QT interval is measured in msec and the RR interval is measured in seconds
QTcF Interval	QTc interval using Fridericia's correction (msec) = $QT/(RR)^{1/3}$, where the QT interval is measured in msec and the RR interval is measured in seconds
RR Interval	Time elapsed between two consecutive R-waves.
SAE	Serious Adverse Event/Experience
SAP	Statistical Analysis Plan
SD	Standard Deviation
SDTM	Standard Data Table Model
SOC	System Organ Class
SOT	Spread of Toxin
SpO2	Peripheral Capillary Oxygen Saturation
SRC	Safety Review Committee
SVC	Slow Vital Capacity
TEAE	Treatment Emergent Adverse Event
WHO	World Health Organization

1. PURPOSE OF THE ANALYSES

This statistical analysis plan (SAP) is based on protocol number EB001-ABD201 Amendment 3 Final Version 4.0 (09May2018) from Bonti, Inc. The SAP will be signed off before the final database lock. The SAP contains detailed information to aid in the performance of the statistical analysis and reporting of the study data for use in the final clinical study report (CSR). This SAP is being written with due consideration of the recommendations outlined in the most recent International Conference on Harmonization (ICH) E9 Guideline entitled Guidance for Industry: Statistical Principles for Clinical Trials, the most recent ICH E3 Guideline and the Guidance for Industry: Structure and Content of Clinical Study and the most recent FDA draft Guidance for Industry - Analgesic Indications: Developing Drug and Biological Products, dated February 2014.

This SAP describes the data sets that will be analyzed and the subject characteristics, safety, and efficacy assessments that will be evaluated. This SAP provides details of the specific statistical methods that will be used. If additional analyses are required to supplement the planned analyses described in this SAP, they may be completed and will be identified in the CSR.

The study was terminated early as per Sponsor's discretion. The decision was not related to any safety findings of the drug. Due to early termination of the study, descriptive summaries will be provided but no statistical comparisons will be performed for the data collected prior to the study close-out.

2. PROTOCOL SUMMARY

2.1 Study Objectives

[REDACTED]

2.1.2 *Efficacy*

To evaluate the efficacy of intraoperative administration of EB-001 IM into the RA muscles in reducing the pain and use of rescue pain medications in subjects undergoing elective abdominoplasty surgery. Efficacy will be assessed by efficacy endpoints listed in [Sections 7.2.1](#) and [7.2.2](#) of the SAP.

2.2 Overall Study Design and Plan

This was planned to be a two-stage study but was terminated after 23 subjects were randomized in Stage 1. The following describes the original study design. The study was intended to be conducted at up to two surgical centers that specialize in elective abdominoplasty surgeries and to enroll up to 32-74 subjects in Stage 1 and 66 subjects in Stage 2, with up to 56-60 subjects

exposed to active drug. The study included a screening visit to determine subject eligibility. On the day of surgery, subjects were admitted to an inpatient clinic for 5 days post-operatively (Days 1-5). Intraoperatively, a single dose of EB-001 IM was given via IM injections into each RA muscles per the surgical procedure manual. Follow up visits were planned to be scheduled at days 8, 15, and 29.

The first stage was a placebo-controlled, single-blind (to subject and staff at study site), single ascending cohort study stratified by ethnicity (Hispanic and non-Hispanic) starting from Cohort 2. Four cohorts (8 subjects per cohort) were planned to be dosed at 4 ascending doses of EB-001. An optional Cohort 5 was to be considered. See [Section 2.4.3](#) of the SAP for planned cohort details.

In the event an intolerable dose was identified, a lower (intermediary) dose could have been evaluated as proposed by the SRC. This lower dose could have been a repeat of the prior lower dose cohort or an intermediary dose between the intolerable dose and prior lower dose cohort.

In the first stage of the study, if an intolerable dose was identified (see Section 4.1.1 of Protocol), a lower dose could be evaluated as proposed by the SRC. This lower dose may be a repeat of the prior lower dose cohort or an intermediary dose between the intolerable dose and prior lower dose cohort. If the dose was an intermediary dose, a sentinel group consisting of 3 subjects (1 active: 2 placebo) would be dosed first. The SRC would review all available safety data of the prior sentinel group through at least Day 5 post-operatively, and 5 additional subjects (3 active: 2 placebo) would be dosed upon approval.

In addition, if the SRC deemed appropriate, before an intolerable dose was identified, a repeat dose, or a dose not exceeding the planned dose of the next cohort could have been evaluated.

If a repeat or lower dose (i.e., any dose at or lower than prior highest dose evaluated without meeting stopping criteria) was to be considered, subjects could be dosed without implementing sentinel dosing strategy.

All dose escalation/adjustments or additional cohorts and corresponding sample size were intended to be and were determined by the SRC.

The second stage was to be a randomized, placebo-controlled, double-blind, parallel 3-arm study. In this stage, there would be 2 doses of EB-001 (to be determined by the SRC after last dosing of last subject of Stage 1) and placebo in a 1:1:1 ratio for a total of 66 subjects stratified by ethnicity (Hispanic and non-Hispanic). The SRC would meet periodically to review safety data.

The study was terminated early (after 23 subjects were randomized and dosed) at the discretion of the sponsor.

2.3 Study Population

The study population consists of healthy males or females 23 to 55 years of age, inclusive, undergoing elective abdominoplasty surgery (Full length plication from xiphoid to pubis, removal of skin/fat flap) under general anesthesia (endotracheal or otherwise) without liposuction.

2.4 Treatment Regimens

[REDACTED]

[REDACTED]

[REDACTED]

[REDACTED]

2.4.2 Comparator Group

[REDACTED]

2.4.3 Planned Dose Cohorts

The planned cohorts were as follows:

Cohort 1 sentinel group (3 subjects; 1 active: 2 placebo) [REDACTED] The rest of the cohort (5 subjects; 3 active: 2 placebo) will be dosed at the same dose after review of all available data by the Safety Review Committee (SRC) is conducted, with safety data through at least Day 5 post-operatively.

Cohort 2 sentinel group (3 subjects; 1 active: 2 placebo) [REDACTED] after review of all available safety data from the prior cohort through at least Day 5 post-operatively. The rest of the cohort (5 subjects; 3 active: 2 placebo) will be dosed after review of all available data by the SRC is conducted, with safety data through at least Day 5 post-operatively.

Cohort 3 sentinel group (3 subjects; 1 active: 2 placebo) [REDACTED] after review of all available safety data from the prior cohorts through at least Day 5 post-operatively. The rest of the cohort (5 subjects; 3 active: 2 placebo) were to be dosed after review of all available data by the SRC was conducted, with safety data through at least Day 5 post-operatively.

Optional Cohort 4 sentinel group (3 subjects; 1 active: 2 placebo) [REDACTED] after review of all available safety data from the prior cohorts through at least Day 5 post-operatively. The rest of the cohort (5 subjects; 3 active: 2 placebo) will be dosed after review of all available data by the SRC is conducted, with safety data through at least Day 5 post-operatively.

Optional Cohort 5 (up to 42 subjects; 2 active: 1 placebo) will be dosed at a dose previously assessed after review of all available safety data from the prior cohorts through at least Day 5 post-operatively.

In the event an intolerable dose is identified, a lower (intermediary) dose may be evaluated as proposed by the SRC. This lower dose may be a repeat of the prior lower dose cohort or an intermediary dose between the intolerable dose and prior lower dose cohort.

After 23 subjects were randomized (enrollment after Cohort 3 was completed), the study enrollment was on hold and the study was later terminated at the discretion of the sponsor.

3. GENERAL ANALYSIS AND REPORTING CONVENTIONS

This section discusses general policies to be employed in the analysis and reporting of the data from the study. Departures from these general policies are provided in the specific detailed

sections of this SAP. When this situation occurs, the rules set forth in the specific section take precedence over the general policies.

All continuous study assessments will be summarized by treatment and time point (as applicable) using the descriptive statistics n, mean, SD, median, and range (minimum, and maximum). All of the categorical study assessments will be summarized by treatment and time point (as applicable) using frequency counts and rates of occurrence (%). Changes from baseline for continuous outcomes will be presented as their corresponding continuous measures for post-baseline visits. All study data will be listed by treatment dose level, subject, and time point (as applicable). The placebo group will consist of the placebo subjects from each of the different cohorts combined. For all analyses, the pooled set of placebo subjects from the various cohorts will be considered the placebo group.

No preliminary rounding will be performed; rounding will only occur after the analysis. To round, consider the digit to the right of the last significant digit: if <5 , then round down; if ≥ 5 , then round up. Means and medians will be presented with one more decimal place than the precision of the data. SDs will be presented with two more decimal places than the precision of the data. Percentages will be presented with one decimal place. Minimums and maximums will be presented with the same precision as the original data.

The domain (Study data tabulation Model [SDTM]) and analysis (Analysis Data Model [ADaM]) data sets will be taken as input to the [redacted] programs that generate the report-ready tables, figures and listings. The submission ready SDTM and ADaM data sets will be provided to the sponsor along with display deliveries.

For all summaries, the pooled set of placebo subjects from the various cohorts will be considered the placebo group.

No testing will be conducted due to early termination of the study.

The following conventions will be used throughout the study analysis:

- Stop Time of dose administration is considered time 0.
- Assessment visit times are defined by time of treatment administration.
- Baseline value is defined as the last valid measurement prior to the start treatment administration.
- Change from baseline is defined as post-baseline value minus baseline value.
- Duration of an AE will be computed in hours in the first 96 hours during confinement and thereafter in days as the stop date of the event minus the start date plus 1. If reported as ongoing at the time of database lock, the stop date will be imputed as the date of the last visit or the last date of any AE for the subject in the database, whichever is later. Other missing dates will be imputed as described in [Table 8-1](#).
- The number of days in the study is computed as: [Date of study completion or withdrawal minus the date of treatment administration (Day 0)] + 1.
- If duplicate values are obtained at a given visit (e.g., repeated vital sign measurements), the last value will be used unless it is noted that the measurement was in error for that value. Values that compromise interpretation will not be used in summaries (e.g., values

that were obtained post-dose will not be summarized as pre-dose values).

- If a pre-rescue NPRS is recorded in the same minute as a rescue medication is recorded, the NPRS will be assumed to have occurred PRIOR to the administration of rescue.
 - If a subject experiences inadequate analgesic relief and takes non- protocol specified rescue medication, they will be treated as 'discontinued' from the efficacy portion of the study. The date/time of the discontinuation will be assumed to be the date/time of the start of non-protocol specified rescue captured on protocol deviations eCRF. Early discontinuation from the efficacy portion affects the computation of the analgesic endpoints only.

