## **8.3 Time Period and Frequency for Event Assessment and Follow-up**

The occurrence of an AE or SAE may come to the attention of study personnel during study visits and interviews of a study participant presenting for medical care, or upon review by a study monitor. All AEs including local and systemic reactions not meeting the criteria for SAEs will be captured on the appropriate eCRF. Information to be collected includes event description, dates and times of onset and resolution, clinician’s assessment of severity, assessment of relatedness to study drug (assessed only by those with the training and authority to make a diagnosis), and action taken. All AEs occurring while on study must be documented appropriately regardless of relationship. All AEs will be followed to adequate resolution.

Any medical condition that is present at the time that the participant is screened will be considered as baseline and not reported as an AE. However, if the study participant’s condition deteriorates at any time during the study, it will be recorded as an AE. UPs will be recorded in the data collection system throughout the study.

Changes in the severity of an AE will be documented to allow an assessment of the duration of the event at each level of severity to be performed. AEs characterized as intermittent require documentation of onset and duration of each episode.

The Investigator will record all reportable events with start dates occurring any time after informed consent is obtained until the AE has resolved, stabilized, or a new chronic baseline has been established. At each study visit, the Investigator will inquire about the occurrence of AE/SAEs since the last visit. Events will be followed for outcome information until resolution or stabilization.

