## **8.8 Risk Management of Prolonged Respiratory Compromise**

Subjects may develop adverse effects indicative of spread of toxin, including a potentially prolonged course of respiratory compromise. If there were to be a significant respiratory event, the study site is located inside an acute care hospital. All subjects have access 24/7 to a fully-functional code blue team (including personnel expert in managing airways and respiratory emergencies). In addition, the study site is located 100 yards from the hospital emergency room so subjects can be quickly and easily transferred after stabilization by the code team.

If there is any significant respiratory event in the study i.e., profound hypoxia, respiratory depression, sedation etc., the study site and staff will follow usual standard of care which may include verbal and physical stimulation, high flow oxygen via face mask or big-mask, airway management, and calling for the hospital code team for immediate transfer to the emergency room once stabilized, if required. Subjects who do not respond to these measures may require endotracheal intubation and mechanical ventilation. Opiate reversal agents may be used in subjects who received opioid rescue medications.

In addition, systemic toxicity of EB-001 may be treated with a multi-valent anti-toxin.

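### An adverse event still ongoing at database lock gets an imputed stop date, so a minimum duration is presented as a completed one (minor in this study)

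*SAP*

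**What the plan says.** SAP Section 3 sets the duration rule: "Duration of an AE will be computed in hours in the first 96 hours during confinement and thereafter in days as the stop date of". Written out, the count in days is stop minus start plus 1. The same bullet also covers an event that has not ended: "If reported as ongoing at the time of database lock, the stop date will be imputed as the date of the last visit or the". It then names a second candidate: "last date of any AE for the subject in the database, whichever is later". The imputed stop is therefore the later of two dates, not simply the last visit. For the rest, "Other missing dates will be imputed as described in" Table 8-1, which is not in the public text.

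Protocol Section 8.3 keeps following events after the scheduled visits. The investigator records events "until the AE has resolved, stabilized, or a new chronic baseline has been established", and "Events will be followed for outcome information until resolution or stabilization". The same section collects both dates and times of onset and resolution. The last planned visit is Day 29.

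SAP Sections 1, 2.2 and 3 say that the study stopped after 23 subjects were randomized and dosed, and that the analysis is descriptive with no testing.

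**The concern.** An event ongoing when last recorded has a right-censored duration: all that is known is that it lasted at least so long. The SAP rule turns that minimum into a completed duration, and nothing in the visible text flags it as different from an observed one. Resolved and unresolved events are then handled unequally. A resolved event keeps its real stop date however late that falls, while an unresolved one is cut at a date when it had not ended.

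Duration bears on this drug's main risk. Protocol Section 8.8 warns of spread-of-toxin effects "including a potentially prolonged course of respiratory compromise", and the protocol's discussion of botulism after Table 3 expects recovery from systemic toxicity to begin about 1 week after dosing. Events that do not resolve are the most informative about that expectation, and they are the ones whose durations are understated.

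The bullet also changes scale at 96 hours, from hours to inclusive calendar days, and gives no unit for an event that starts before that point and ends after it.

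**Working it through.** The plan states no figure for this point, so there is none to reproduce. The check applies the SAP's own rule to hypothetical dates.

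**Inputs.** The stop-date and duration rules are from SAP Section 3. The last planned visit, Day 29, is from SAP Section 2.2. Follow-up past Day 29 is from Protocol Section 8.3. Onset, resolution and withdrawal days are assumed for illustration.

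**Formulas.** Imputed stop = max(last visit, last date of any AE for the subject). Duration in days = stop − start + 1.

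1. *Different subjects, same onset.* Subject A: onset Day 2, resolved Day 45, so 45 − 2 + 1 = 44 days. Subject B: onset Day 2, ongoing, last visit Day 29, no later AE date, so 29 − 2 + 1 = 28 days. The unresolved event is reported as 44 − 28 = 16 days shorter.
2. *Same subject, same onset.* If one subject has both events, the imputed stop is max(29, 45) = Day 45, and both get 44 days. The gap is 0. Within a subject and for equal onset, an ongoing event cannot come out shorter than a resolved one.
3. *Another onset day, different subjects.* Onset Day 20: ongoing gives 29 − 20 + 1 = 10 days; resolved on Day 40 gives 40 − 20 + 1 = 21 days.
4. *Early withdrawal or late onset.* Onset Day 2, last visit Day 8, no later AE date: 8 − 2 + 1 = 7 days. Onset Day 27, last visit Day 29, no later AE date: 29 − 27 + 1 = 3 days. These are the cases in which an unresolved event gets a very short duration.
5. *Unit change.* A 1-hour event in the first 96 hours is recorded as 1 hour. After that it is 1 day if it falls on one date (6 − 6 + 1) and 2 days if it crosses midnight (7 − 6 + 1). This distorts a result only if hours and inclusive days are pooled. The SAP does not equate an inclusive day with 24 hours, and no visible text pools the two.

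**The case against.** The strongest case against is that little depends on this rule. There are 23 subjects, with four active subjects planned in each of the three completed cohorts (SAP Section 2.4.3). Nothing is tested, and no visible endpoint uses AE duration. SAP Section 3 lets specific sections override its general conventions. The AE analysis section is not in the public text, so it may already flag ongoing events, or durations may only be listed. All study data are listed by subject, and Protocol Section 8.5.1 requires a chronological narrative and continued follow-up for serious events, so a prolonged serious respiratory event would not be judged by a derived duration alone. All of this stands and sets the size of the point. It does not make the stated rule correct.

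Three stronger readings are tempting, and the documents do not support them.

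- *The stop date is always the last visit.* The rule takes the later of two dates, which removes the understatement in case 2 and reduces it wherever the subject has a later AE date.
- *Durations are understated by months, up to database lock.* The documents give no lock date. An event reported as ongoing carries its last recorded status, which does not show that it was observed on the day of lock.
- *The rule hides evidence against recovery beginning at about 1 week.* In a completer with early onset the imputed value is still about four weeks (28 days in case 1), which visibly contradicts that expectation.

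**Conclusion.** The point holds as a minor one. SAP Section 3 presents minimum durations of unresolved events as completed durations, and such an event can be reported as shorter than a resolved one in another subject: 28 against 44 days in the worked example. That gap requires different subjects, a resolved event followed past Day 29, and no later AE date in the subject whose event is ongoing. The direction is fixed: an event known to be continuing is never overstated, and any error shortens it. How many events are affected cannot be known from the documents, nor whether durations are summarised or only listed. The change of unit is a secondary matter. It counts only if the two scales are combined or an event crosses 96 hours, for which no rule is visible.

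**What to change.** In SAP Section 3, remove the stop-date imputation for events ongoing at lock. List each as ongoing, at least x days, with x counted from onset to the last date on which the event was confirmed ongoing. Do not count to database lock, which would claim a minimum that nobody observed. Give the number of ongoing events by treatment group, and keep them out of any summary of resolved durations. With so few subjects, a count beside the resolved durations is enough, and a survival-type summary would add nothing useful.

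Compute duration for all events on one scale from the collected onset and resolution dates and times. That also settles events that cross 96 hours.

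The cost is one or two SAP sentences and a small programming change. Onset and resolution dates and times are already collected, and follow-up of subjects does not change. The one downside is that an ongoing event no longer has a single duration value.
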